| | Baseline for POEM Total Score by Age | | |
| | Group | | |
| 14.2.1.6.4 | Summary of Values and Change from | PP | Repeat |
| | Baseline for POEM Total Score by Age | | |
| | Group | | |
| 14.2.1.6.5 | Summary of Values and Change from | mITT | Repeat |
| | Baseline for POEM Total Score by Sex | | |
| 14.2.1.6.6 | Summary of Values and Change from | PP | Repeat |
| | Baseline for POEM Total Score by Sex | | |
| 14.2.1.6.7 | Summary of Values and Change from | mITT | Repeat |
| | Baseline for POEM Total Score by | | |
| | Race | | |
| 14.2.1.6.8 | Summary of Values and Change from | PP | Repeat |
| | Baseline for POEM Total Score by | | |
| | Race | | |

| 14.2.1.6.9 | Summary of Values and Change from | mITT | Repeat |
|-------------|--|------|--------|
| | Baseline for POEM Total Score by Baseline IGA | | |
| 14 2 1 6 10 | Summary of Values and Change from | рр | Reneat |
| 17.2.1.0.10 | Baseline for POEM Total Score by | 11 | Repour |
| | Baseline IGA | | |
| 14.2.1.6.11 | Summary of Values and Change from | mITT | Repeat |
| | Baseline for POEM Total Score by | | - |
| | Baseline EASI | | |
| 14.2.1.6.12 | Summary of Values and Change from | PP | Repeat |
| | Baseline for POEM Total Score by | | |
| | Baseline EASI | | |
| 14.2.1.6.13 | Summary of Values and Change from | mITT | Repeat |
| | Baseline for POEM Total Score by | | |
| | Baseline BSA | | |
| 14.2.1.6.14 | Summary of Values and Change from | PP | Repeat |
| | Baseline for POEM Total Score by | | |
| | Baseline BSA | | |
| 14.2.1.6.15 | Summary of Values and Change from | mITT | Repeat |
| | Baseline for POEM Total Score by | | |
| | Rescue Medication Status at Baseline | | |
| 14.2.1.6.16 | Summary of Values and Change from | PP | Repeat |
| | Baseline for POEM Total Score by | | |
| | Rescue Medication Status at Baseline | | |
| 14.2.1.6.17 | Summary of Values and Change from | mITT | Repeat |
| | Baseline for POEM Total Score by | | |
| | Rescue Medication Status on Treatment | | |
| 14.2.1.6.18 | Summary of Values and Change from | PP | Repeat |
| | Baseline for POEM Total Score by | | |
| | Rescue Medication Status on Treatment | | |
| 14.2.1.7.1 | Shift from Baseline for IGA | mITT | Unique |
| 14.2.1.7.2 | Shift from Baseline for IGA | PP | Repeat |
| INFERENTIAL | | | |

| 14.2.2.1 | Mean Change in WI-NRS from | mITT | Unique |
|------------|--------------------------------------|------|--------|
| | Baseline to Week 4 – ANCOVA | | |

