|----------------------|--------|--------------|-----------|-----------|--------------|---------------|-----------|-----------|
| Treatment Group | Visit | Visit Value | Statistic | Clear | Almost Clear | Mild | Moderate | Severe |
| B244 O.D. 5.0 | Week 2 | Clear [1,2] | n (%) | xx (xx.x) | xx (xx.x) | xx (xx.x) | xx (xx.x) | xx (xx.x) |
| (N=xx) | | Almost Clear | n (%) | xx (xx.x) | xx (xx.x) | xx (xx.x) | xx (xx.x) | xx (xx.x) |
| | | Mild | n (%) | xx (xx.x) | xx (xx.x) | xx (xx.x) | xx (xx.x) | xx (xx.x) |
| | | Moderate | n (%) | xx (xx.x) | xx (xx.x) | xx (xx.x) | xx (xx.x) | xx (xx.x) |
| | | Severe | n (%) | xx (xx.x) | xx (xx.x) | xx (xx.x) | xx (xx.x) | xx (xx.x) |
| | | Clear | n (%) | xx (xx.x) | xx (xx.x) | xx (xx.x) | xx (xx.x) | xx (xx.x) |
| | Week 4 | Almost Clear | n (%) | xx (xx.x) | xx (xx.x) | xx (xx.x) | xx (xx.x) | xx (xx.x) |
| | | Mild | n (%) | xx (xx.x) | xx (xx.x) | xx (xx.x) | xx (xx.x) | xx (xx.x) |
| | | Moderate | n (%) | xx (xx.x) | xx (xx.x) | xx (xx.x) | xx (xx.x) | xx (xx.x) |
| | | Severe | n (%) | xx (xx.x) | xx (xx.x) | xx (xx.x) | xx (xx.x) | xx (xx.x) |
| | | Clear | n (%) | xx (xx.x) | xx (xx.x) | xx (xx.x) | xx (xx.x) | xx (xx.x) |
| | | Almost Clear | n (%) | xx (xx.x) | xx (xx.x) | xx (xx.x) | xx (xx.x) | xx (xx.x) |
| Repeat for B244 O.D. | Week 8 | Mild | n (%) | xx (xx.x) | xx (xx.x) | xx (xx.x) | xx (xx.x) | xx (xx.x) |
| 20.0, Pooled B244, | | Moderate | n (%) | xx (xx.x) | xx (xx.x) | xx (xx.x) | xx (xx.x) | xx (xx.x) |
| and Vehicle | | Severe | n (%) | xx (xx.x) | xx (xx.x) | xx (xx.x) | xx (xx.x) | xx (xx.x) |

Table 14.2.1.7.1 Shift from Baseline for IGA (Safety Population)

[1] Percentage and all subsequent percentages based on the number treated.
 [2] 0=Clear, 1=Almost Clear, 2=Mild, 3=Moderate, 4=Severe.
 Source: Listing XXXX
 PROGRAM NAME: XXXXXXXXX

DATE: HH:MM/DDMMMYYYY

Programming Note:

• Repeat for 14.2.1.7.2 Shift from Baseline for IGA for PP Population

| | | | B244 O.D. 5.0 | B244 O.D. 20.0 | Pooled B244 | Vehicle |
|----------------|----------------|----------------------|---------------|----------------|---------------|---------------|
| Visit | Statistic Type | Statistic | (N=xx) | (N=xx) | (N=xx) | (N=xx) |
| Week 4 CFB [1] | ANCOVA [2,3] | n | XX | XX | XX | XX |
| | | LSM (SE) [4] | xx.x (xx.xxx) | xx.x (xx.xxx) | xx.x (xx.xxx) | xx.x (xx.xxx) |
| | | 95% CI | (xx.x, xx.x) | (xx.x, xx.x) | (xx.x, xx.x) | (xx.x, xx.x) |
| | v. Vehicle | | | | | |

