As a parallel to the non-responder imputation analysis, for score-based endpoints of WI-NRS, AI-NRS, IGA, and EASI, we will perform worst-value imputation on/after the date of first ontreatment rescue medication or date of subject early discontinuation through the end of the study. For this sensitivity analysis, all values on/after the date of first on-treatment rescue medication use or all values missing due to subject early discontinuation will be replaced with the worst value observed for each subject between first post-baseline assessment and first use of ontreatment rescue medication (WOCF). In the event there is no observation after baseline recorded, WOCF will be Baseline values.

Subjects who discontinue early should have (1) at least one treatment-emergent adverse event (TEAE) leading to discontinuation and (2) discontinuation occurring prior to their Week 4 visit in order to have their data imputed for WOCF analysis.

In cases where subjects completed the treatment period, but did not complete all of the follow-up period, the following logic will be used in order to fully parallel the NRI analysis. If subjects use rescue medications while on treatment and discontinue after the Week 4 visit, then only values from first on-treatment rescue medication use through last attended visit will be imputed with WOCF (i.e., missing data from visits that did not occur after Week 4 would not be imputed in this case).

The mITT population will be used for this analysis. For WOCF imputation of WI-NRS and AI-NRS values, the worst-observation would be the highest weekly average (not highest daily score) reported after baseline and before first on-treatment rescue medication use or before subject early discontinuation.

ADDENDUM TO SAP v3.0

Version 1.0 22-Apr-22

If a situation occurs where a visit is missed but a subsequent visit takes place for the same subject, then the missing data for that interim visit will not be imputed unless that visit occurs on/after the date of first on-treatment medication use.

3 Request 2: Intention-to-Treat Analysis

FDA Request: We recommend that you perform additional sensitivity analyses to include dropouts for whom no single score is collected and thus missing data handling strategies are to be considered. In this analysis, the analysis population will be the intent-to-treat (ITT) population.

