To approximate an intent-to-treat population, LOCF methods will be applied for all randomized subjects missing Week 4 responses for endpoints (WI-NRS, AI-NRS, IGA, EASI, and responder analyses). Subjects missing Week 4 values will have their measurement imputed to be the LOCF value on treatment or baseline, whichever is later. Sensitivity analysis of WI-NRS, AI-NRS, IGA, EASI, and related responder analyses will be performed.

Intention-to-Treat Population (ITT): All subjects who were randomized, regardless of exposure to treatment.

For subjects who were randomized, but did not receive treatment, the baseline WI-NRS and AI-NRS scores will be calculated using the same approach that is used for treated subjects (as described in section 6.4 of the SAP), except that the reference date will be the date of the baseline visit instead of the date of first dose.

ADDENDUM TO SAP v3.0

Version 1.0 22-Apr-22

4 List of Tables

| Display Number | Title | Population | Unique/ | Request |
|----------------|---|------------|---------|---------|
| | | | Repeat | # |
| 14.2.2.2a | Mean Change in WI-NRS from Baseline to Week 4 – ANCOVA - WOCF | mITT | Repeat | 1 |
| 14.2.2.2b | Mean Change in WI-NRS from Baseline to Week 4 – ANCOVA – WOCF Sensitivity | mITT | Repeat | 1 |
| 14.2.2.2c | Mean Change in WI-NRS from Baseline to Week 4 – ANCOVA - LOCF | ITT | Repeat | 2 |
| 14.2.2.3.4a | Mean Change in WI-NRS from Baseline to Weeks 1 Through 8 - WOCF | mITT | Repeat | 1 |
| 14.2.2.3.4b | Mean Change in WI-NRS from Baseline to Weeks 1 Through 8 - WOCF Sensitivity | mITT | Repeat | 1 |
| 14.2.2.4.4a | Mean Change in AI-NRS from Baseline to Weeks 1 Through 8 - WOCF | mITT | Repeat | 1 |
| 14.2.2.4.4b | Mean Change in AI-NRS from Baseline to Weeks 1 Through 8 - WOCF Sensitivity | mITT | Repeat | 1 |
| 14.2.2.4.9 | Mean Change in AI-NRS from Baseline to Week 4 - LOCF | ITT | Repeat | 2 |
| 14.2.2.5.13 | Proportion of Subjects with ≥4 Point Improvement in WI-NRS from Baseline to Week 4 - LOCF | ITT | Repeat | 2 |
| 14.2.2.7.13 | Proportion of Subjects with ≥4 Point Improvement in AI-NRS from Baseline to Week 4 - LOCF | ITT | Repeat | 2 |
| 14.2.2.10.2a | Mean Change in EASI Total Score from Baseline to Weeks 2, 4, and 8 - WOCF | mITT | Repeat | 1 |
| 14.2.2.10.5 | Mean Change in EASI Total Score from Baseline to Week 4 - LOCF | ITT | Repeat | 2 |
| 14.2.2.11.2a | Mean Change in IGA from Baseline to Weeks 2, 4, and 8 - WOCF | mITT | Repeat | 1 |

ADDENDUM TO SAP v3.0

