- Repeat for 14.2.2.4.9 Mean Change in AI-NRS from Baseline to Week 4 LOCF for ITT Population
 - First column will contain only "Week 4 CFB [1]"
 - Add new footnote "Note: LOCF = Last Observation Carried Forward." as the first footnote.
 - Footnote [3] will be "Model uses a compound symmetry covariance structure and contains treatment group and baseline AI-NRS as explanatory variables, where baseline AI-NRS = (Sum of daily AI-NRS scores from Day -7 to Day -1) / (Total number of AI-NRS diaries entered from Day -7 to Day -1) and at least one AI-NRS daily score is reported between Days -7 and -1 and for the corresponding week. All subjects who meet ITT criteria are included and no data is excluded based on rescue medication use. Any values missing at Week 4 will be imputed using LOCF."

Protocol: PRB244-01 Confidential

ADDENDUM TO SAP v3.0

Version 1.0 22-Apr-22

Table 14.2.2.5.13 Proportion of Subjects with ≥4 Point Improvement in WI-NRS from Baseline to Week 4 – LOCF (ITT Population)

| Visit | Statistic Type | Statistic | B244 O.D. 5.0 (N=xx) | B244 O.D. 20.0 (N=xx) | Pooled B244 (N=xx) | Vehicle (N=xx) |
|--------|----------------|----------------------------------|------------------------------|------------------------------|------------------------------|------------------------------|
| Week 4 | Logistic [1,2] | n/N (Proportion %) [3] 95% CI | xx/xx (xx.x) (xx.x, xx.x) | xx/xx (xx.x) (xx.x, xx.x) | xx/xx (xx.x) (xx.x, xx.x) | xx/xx (xx.x) (xx.x, xx.x) |
| | v. Vehicle | Odds Ratio (95% CI) p-value | x.xx (x.xx, x.xx) x.xxxx | x.xx (x.xx, x.xx) x.xxxx | x.xx (x.xx, x.xx) x.xxxx | N/A N/A |
| | 20.0 v 5.0 | Odds Ratio (95% CI) p-value | N/A N/A | x.xx (x.xx, x.xx) x.xxxx | N/A N/A | N/A N/A |

Note: LOCF = Last Observation Carried Forward.

[1] Logistic regression model contains treatment group as the explanatory variable. At least one WI-NRS daily score is reported between Days -7 and -1 and for the corresponding week. All subjects who meet ITT criteria are included and no data is excluded based on rescue medication use. Any values missing at Week 4 will be imputed using LOCF. [2] Treatment response is improvement by \geq 4 Points in WI-NRS score (i.e., decrease in WI-NRS score by at least 4 points from Baseline to Post-Baseline visit).

[3] n is the number of subjects who have improved at that visit. N is the number of subjects with data at that visit, regardless of improvement status.

Source: Listing XXXX

PROGRAM NAME: XXXXXXXXXX

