DATE: HH:MM/DDMMMYYYY

Programming Note:

• Repeat for 14.2.2.7.13 Proportion of Subjects with ≥4 Point Improvement in AI-NRS from Baseline to Week 4 – LOCF for mITT Population

• Add new footnote "Note: LOCF = Last Observation Carried Forward." as the first footnote.

Footnote [1] will be same as in 14.2.2.5.13, except changing "WI-NRS" to "AI-NRS"

Protocol: PRB244-01 Confidential

ADDENDUM TO SAP v3.0

Version 1.0 22-Apr-22

Table 14.2.2.10.2a Mean Change in EASI Total Score from Baseline to Weeks 2, 4, and 8 – WOCF (mITT Population)

| Visit | Statistic Type | Statistic | B244 O.D. 5.0 (N=xx) | B244 O.D. 20.0 (N=xx) | Pooled B244 (N=xx) | Vehicle (N=xx) |
|--------------------------|----------------|--|---|---|---|-------------------------------------|
| Week 2 CFB [1] | MMRM [2,3] | n LSM (SE) [4] 95% CI | xx xx.x (xx.xxx) (xx.x, xx.x) | xx xx.x (xx.xxx) (xx.x, xx.x) | xx xx.x (xx.xxx) (xx.x, xx.x) | xx xx.x (xx.xxx) (xx.x, xx.x) |
| | v. Vehicle | LSM Difference (SE) 95% CI p-value | xx.x (xx.xxx) (xx.x, xx.x) x.xxxx | xx.x (xx.xxx) (xx.x, xx.x) x.xxxx | xx.x (xx.xxx) (xx.x, xx.x) x.xxxx | N/A N/A N/A |
| Repeat for Weeks 4 and 8 | 20.0 v 5.0 | LSM Difference (SE) 95% CI p-value | N/A N/A N/A | xx.x (xx.xxx) (xx.x, xx.x) x.xxxx | N/A N/A N/A | N/A N/A N/A |

Note: WOCF = Worst Observation Carried Forward.

[1] CFB = Change from Baseline.

[2] MMRM = Mixed Model with Repeated Measures.

[3] Model uses a compound symmetry covariance structure and contains visit, treatment group, visit-by-treatment interaction, and baseline EASI total score as explanatory variables. All subjects who meet mITT criteria are included. Data collected from the week of first on-treatment rescue medication use through the end of the study and missing data due to subject dropout will be imputed using WOCF. Data collected prior to the week of first on-treatment rescue medication use or dropout will be included.

[4] LSM = Least Squares Mean. SE = Standard Error.

Source: Listing XXXX

PROGRAM NAME: XXXXXXXXXX

Programming Note:

- Repeat for 14.2.2.10.5 Mean Change in EASI Total Score from Baseline to Week 4 LOCF for ITT Population
 - First column will contain only "Week 4 CFB [1]"
 - Add new footnote "Note: LOCF = Last Observation Carried Forward." as the first footnote.

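### The Addendum contradicts itself on the population for the AI-NRS responder LOCF table (14.2.2.7.13): the programming note's heading says mITT, everything else says ITT

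*SAP*

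**What the plan says.** **The request and the response.** Section 3 of the Addendum records the FDA's second request: sensitivity analyses that bring in dropouts with no score at all. On the population it says "In this analysis, the analysis population will be the intent-to-treat (ITT) population". The sponsor's reply in the same section applies LOCF to all randomised subjects with no Week 4 value, names AI-NRS and the responder analyses, and defines ITT as everyone randomised, whether or not exposed to treatment.

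**The table.** The Addendum's list of tables (Section 4) has, for 14.2.2.7.13, "Proportion of Subjects with ≥4 Point Improvement in AI-NRS from Baseline to Week 4 - LOCF | ITT", under Request 2. The programming note in Section 5 that generates the table from 14.2.2.5.13 is headed "Improvement in AI-NRS from Baseline to Week 4 – LOCF for mITT Population". The same note keeps footnote [1] of 14.2.2.5.13 and changes only WI-NRS to AI-NRS. That footnote says "All subjects who meet ITT criteria are included and no data is excluded based on rescue medication use". It also requires at least one daily score both in the week before baseline and in the corresponding post-baseline week.

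**The mITT set.** SAP Section 7.2.4 limits mITT to randomised subjects with at least one dose and at least one on-site evaluation after baseline.

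**A separate label conflict.** In the SAP's efficacy table list, 14.2.1.7.1 appears as "Shift from Baseline for IGA | mITT | Unique". Its shell is titled "Table 14.2.1.7.1 Shift from Baseline for IGA (Safety Population)".

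**The concern.** A programming note is an operative instruction: it tells the programmer which population flag to apply. Here one note carries two, mITT in its heading and ITT in its footnote. Followed literally, it would produce a table titled mITT with a footnote claiming ITT.

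The two sets differ on the subjects the request was about. A randomised subject who was never dosed, or who was dosed and then lost before any on-site visit, is in ITT and not in mITT. If the heading wins, the table loses these subjects, does not deliver what Section 3 promises, and cannot be read beside the WI-NRS responder table, which is on ITT. The AI-NRS proportion with at least 4 points of improvement is a listed secondary endpoint (SAP Section 3.2.2), so the two tables will naturally be compared.

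**Working it through.** **1. Which places say what, for Table 14.2.2.7.13**

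| Place in the Addendum | Population |
|---|---|
| Section 3, FDA request | ITT |
| Section 3, sponsor's reply and definition | ITT, all randomised |
| Section 4, list of tables | ITT |
| Section 5, programming note, heading | mITT |
| Section 5, same note, carried-over footnote [1] | ITT |

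One line says mITT and four say ITT. The other Request 2 shells and notes in the text available all say ITT: WI-NRS ANCOVA, AI-NRS mean change, WI-NRS responders, EASI mean change, IGA mean change and EASI-75. Nearby notes also contain numbering slips. The WI-NRS ANCOVA LOCF table is 14.2.2.2c in the list and 14.2.2.2e in its note. The IGA mean-change LOCF table is 14.2.2.11.5 in the list and 14.2.2.10.5 in its note. The mITT heading looks like another slip of this kind.

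**2. What the mITT reading would do to the rate**

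Let p be the ITT response rate in an arm, f the fraction of ITT subjects outside mITT, and e the LOCF response rate among those omitted. Then

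mITT rate = (p − f·e) / (1 − f), and the change from ITT is f·(p − e) / (1 − f).

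The rate rises when e is below p. A subject with only a baseline value has zero change under LOCF and is a non-responder; if all omitted subjects are like this, e = 0 and the mITT rate is p / (1 − f).

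The documents give neither p nor f. The only related planning figure is dropout of 16.7%, which reproduces: 1 − 480/576 = 16.7%. That covers loss over the whole study to Week 8, so f should be well below it. The values below are assumptions, with 192 subjects per arm and e = 0.

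| Assumed ITT rate | 2% omitted (4) | 5% omitted (10) | 10% omitted (19) | 16.7% omitted (32) |
|---|---|---|---|---|
| 25% (48/192) | 48/188 = 25.5% | 48/182 = 26.4% | 48/173 = 27.7% | 48/160 = 30.0% |
| 35% (67/192) | 67/188 = 35.6% | 67/182 = 36.8% | 67/173 = 38.7% | 67/160 = 41.9% |

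**3. What it would do to the treatment comparison**

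Assume ITT rates of 35% on active and 22% on vehicle. The odds ratio is (0.35/0.65) / (0.22/0.78) = 1.91.

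- Omit 10% on active and 5% on vehicle: rates 0.35/0.90 = 38.9% and 0.22/0.95 = 23.2%, odds ratio 2.11.
- Omit 5% on active and 10% on vehicle: rates 0.35/0.95 = 36.8% and 0.22/0.90 = 24.4%, odds ratio 1.80.

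The direction depends on which arm loses more subjects early.

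**4. The carried-over diary condition**

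Read literally, footnote [1] admits only subjects with a diary score in the corresponding week, which for this table is Week 4. A subject with no Week 4 score is the one LOCF is meant to impute. Correcting the heading alone would therefore leave an instruction that removes the same subjects by another route. The footnote for the WI-NRS ANCOVA LOCF table has no such condition; it asks only for a baseline-week score.

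**5. The IGA shift table**

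The Safety set needs one dose and groups subjects as treated (SAP Section 7.2.3). mITT adds the on-site visit requirement and groups as randomised. Safety is thus the wider set. Using it loses no dropouts, and the table reports no response rate that could be inflated.

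**The case against.** The strongest reply is that this is an editing slip with an obvious resolution. The request, the sponsor's reply, the list and the footnote all say ITT, and a careful programmer would follow them. SAP Section 6.3 allows changes to titles, numbering and other minor matters without a SAP revision. The table is one sensitivity analysis of a secondary endpoint whose p-values the SAP already calls exploratory (Section 7.4), and the corresponding WI-NRS tables are consistently ITT.

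Most of that stands, and it limits the importance of the point. It does not remove it: Section 6.3 also says that true differences in data handling need documenting, and the choice of population is such a difference. A programmer should not have to settle it silently.

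Three stronger readings are tempting, and the documents do not support them.

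- *The note settles on mITT.* It does not; its own footnote says ITT.
- *The response rate will rise and favour B244.* This needs the mITT heading to be followed and the omitted subjects to be mainly non-responders. A subject with diary entries but no on-site visit is outside mITT, yet one entry is enough for a weekly average (SAP Section 6.5.3), so that subject could be a LOCF responder. The number omitted may also be small: Protocol Section 8.9 plans a visit within 7 days for subjects who stop treatment early, and if that counts as an on-site evaluation they stay in mITT.
- *The IGA shift table has the same fault.* It is a label conflict only, as step 5 shows. Nor do the documents give a reason to replace that shell's denominator, the number treated, with a per-visit count.

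**Conclusion.** The contradiction is real and sits in an instruction that decides who is analysed. If the mITT heading is followed, Table 14.2.2.7.13 does not answer the FDA's second request and does not match its WI-NRS counterpart. The effect on the reported rate is conditional. With all omitted subjects non-responders and ITT rates of 25% to 35%, the increase is 0.5 to 1.9 points when 2% to 5% are omitted, and 5.0 to 7.0 points in the extreme case where the whole planned 16.7% dropout falls outside mITT. Those rates and fractions are assumptions; the documents supply neither. The treatment contrast has no fixed direction. The primary endpoint and its LOCF analysis are unaffected. This is a minor correction, worth making because it is nearly free.

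**What to change.** 1. In the programming note for Table 14.2.2.7.13, change the population in the heading from mITT to ITT.
2. Reword footnote [1] at its source in Table 14.2.2.5.13, so that the rewording carries into 14.2.2.7.13: require a baseline-week score, and drop the need for a score in the corresponding week when Week 4 is imputed by LOCF. The note for the AI-NRS mean-change LOCF table (14.2.2.4.9) contains the same condition and should be aligned.
3. Separately, retitle shell Table 14.2.1.7.1 to mITT to agree with its list entry, leaving its denominator as it is.

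The cost is text corrections only, with no new data or methods. The AI-NRS responder rate may come out slightly less favourable than it would under mITT.
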